## **CRITERIA FOR SUBJECT ELIGIBILITY**

#### Subject Population

Undergoing elective ureteroscopy with stent placement at University of Missouri Hospital and affiliated facilities

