#### Subject Inclusion

- Age  $\geq$  18 years
- Undergoing ureteroscopy with plan for stent placement

Subject Exclusion

- Renal insufficiency (eGFR < 50 mL/minute/1.73 m^2)
- Ureteral stent in place >30 days
- Chronic opioid use
- History of opioid abuse

- Chronic gabapentinoid use
- History of gabapentinoid abuse
- Plan for inpatient hospitalization either leading up to or after treatment
- Pregnancy
- Inability of the patient to consent for themselves in English
- Allergy to gabapentinoid
- Liver failure or hepatic dysfunction
- No email address that is regularly checked

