#### Participant randomization

Randomization will be undertaken using the randomization module available in REDCap. Patients will be randomized to either "Group A" or "Group B". Medications will be distributed via the investigational pharmacy according to patient allotment. No one outside the investigational pharmacy will have knowledge of which group receives active medication.

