Perioperative pregabalin as part of a multimodal treatment plan for pain after ureteroscopy with stent placement: a randomized, controlled trial

Statistical analysis plan

Version 1.0 Version date: February 27, 2020

Statistical Analysis Plan

Enrolled subjects' characteristics will be summarized using mean \pm SD for continuous variables and proportions for categorical variables. The primary outcome of interest, the value on the visual analog scale of pain score (VAS score), will be summarized overall and by treatment group, those who received perioperative pregabalin and those who received placebo. To examine the research question, an independent sample t-test will be conducted to assess if differences exist on VAS scores by the treatment group. The assumptions of normality and homogeneity of variance will be assessed. Normality of the scores will be assessed using the One-Sample Kolmogorov-Smirnov test. Homogeneity of variance will be assessed using Levene's Test for the Equality of Error Variances. The *t*-test will be two- tailed with the probability of rejecting the null hypothesis when it is true set at *p* < 0.05. If groups are unbalanced with respect to one or more patients' characteristics, we will perform a stratified analysis of VAS scores based on that characteristics.

For the secondary outcomes of interest, a two sample t-test or a Chi-square test of independency will be used to compare the treatment groups for continuous and categorical outcomes, respectively. In addition to univariate analysis, we will fit a generalized linear model or logistic regression model of outcome on treatment group controlling for possible confounding variables such as, gender, age, pre-operation VAS score and pre-operation Watson clock drawing score, depending on type of outcome.

Power Analysis

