Group sample sizes of 59 per group achieve 80% power to reject the null hypothesis of equal means when the population mean difference in VAS score is as little as 1 unit, assuming the standard deviations of 1 for group 1 (based on our pilot study) and 2.5 for group 2 (from literature), and with a significance level (alpha) of 0.05 using a two-sided two-sample unequal-variance t-test. Assumption about 40% dropout rate, it requires approximately 200 total subjects with a planned 1:1 placebo to active treatment enrollment ratio. We estimate at least 500 eligible procedures are conducted each year at our institution. Accounting for excluded patients and those who do not wish to participate, we estimate that full enrollment should be attainable within one year.

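### The SAP adds a stratified analysis of the primary VAS outcome, triggered by chance imbalance, without defining its trigger, method or status

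*SAP*

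**What the plan says.** The SAP's analysis paragraph names the VAS pain score as the primary outcome and plans a two-tailed independent-sample t-test at the 5% level, without condition and without covariates. The same paragraph ends with a conditional rule: "If groups are unbalanced with respect to one or more patients' characteristics, we will perform a stratified analysis of VAS scores", the strata being whatever characteristic proved unequal. Nothing further is said about that analysis.

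Regression models with covariates appear only in the next paragraph, on secondary outcomes. They come with an open list of examples: gender, age, pre-operative VAS and pre-operative clock-drawing score. The protocol's evaluation table shows that pre-operative VAS is collected from every patient.

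The SAP's power section sizes the trial on the unadjusted comparison, "with a significance level (alpha) of 0.05 using a two-sided two-sample unequal-variance t-test", with SDs of 1 and 2.5 in the two groups.

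On allocation, the protocol's section on participant randomization says "Randomization will be undertaken using the randomization module available in REDCap" and mentions neither strata nor blocks. The eligible population is described as "Undergoing elective ureteroscopy with stent placement at University of Missouri Hospital and affiliated facilities". The exclusion list removes patients with "Ureteral stent in place >30 days", so patients with a more recent stent and patients with none can both enter.

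**The concern.** Under randomisation, a baseline difference between the arms is chance. A rule that waits for such a difference selects covariates by how unequal they happen to be. A characteristic unrelated to pain can be selected, while a strong predictor that is only mildly unequal is passed over. Adjustment gains precision and removes chance bias through covariates that predict the outcome, and those can be named in advance.

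The rule also leaves four things open:
- which characteristics are inspected;
- what counts as unbalanced (a p-value, a standardised difference or a judgement);
- whether stratified means one pooled estimate across strata or a separate test in each stratum;
- whether the result outranks, supports or ranks below the t-test.

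The protocol's analysis section defers to a formal SAP, so no other document settles these points. If the two results fall on opposite sides of 5%, the plan does not say which one answers the primary question. What is at stake is selective reporting and interpretation of the primary outcome.

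**Working it through.** **1. The plan's own figure.** Inputs from the SAP's power section: difference 1 unit, SDs 1 and 2.5, two-sided 5%, unequal-variance t-test. For n per arm, the noncentrality is 1/√((1 + 6.25)/n) and the Satterthwaite df is (n − 1) × 7.25²/(1² + 6.25²).
- n = 59: noncentrality 1/√(7.25/59) = 2.85; df = 58 × 52.56/40.06 = 76.1; power 80.4%.
- n = 58: power 79.7%.

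So 59 is the smallest n that reaches 80%, as stated. With 40% dropout, 118/0.60 = 197, or about 200. Both figures reproduce.

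**2. How often the rule would fire.** The SAP gives no criterion. Assume that k independent characteristics are tested and that p < 0.05 counts as unbalanced. The chance of at least one is 1 − 0.95^k: 19% for k = 4, 23% for 5, 26% for 6, 40% for 10, 54% for 15. At p < 0.10 it is 34% for 4, 47% for 6 and 65% for 10.

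**3. Effect on type I error, pooled reading.** Simulated null trials: 59 per arm, balanced binary characteristics, trigger at p < 0.05, stratified analysis taken as one pooled treatment effect adjusted for the triggered characteristics. There were 20,000 runs per row, so the Monte Carlo standard error is √(0.05 × 0.95/20,000) = 0.15 percentage points. The number of characteristics and the share of VAS variance explained are assumed.

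| Characteristics | Variance explained | Triggered | t-test alone | Stratified replaces t-test when triggered | Better of the two | All characteristics prespecified |
|---|---|---|---|---|---|---|
| 1 | 20% | 5.4% | 5.0% | 4.5% | 5.1% | 5.0% |
| 6 | 10% | 27.8% | 5.0% | 4.7% | 5.4% | 4.8% |
| 6 | 30% | 27.5% | 4.9% | 4.2% | 5.5% | 5.1% |
| 10 | 30% | 41.8% | 5.0% | 4.3% | 5.7% | 4.9% |

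A second set, with 5, 10 and 15 characteristics explaining 30% of variance, gave 5.4%, 5.4% and 6.0% for the better of the two. The two tests disagreed on significance in 1.7%, 2.0% and 2.4% of all trials. Both sets used equal error variance in the two arms, so they do not test the robust standard errors proposed below.

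**4. The other reading of stratified.** If it means a separate test in each stratum, the chance under the null of at least one nominally significant VAS result (t-test or any stratum) was 7.0%, 8.7% and 10.1% for 5, 10 and 15 characteristics (8,000 runs, 30% of variance explained). This counts every stratum result as a claim, so it is an outer figure. Under the SAP's own assumptions a half-size stratum of about 30 per arm has noncentrality 1/√(7.25/30) = 2.03 and power of about 51%, against 80% overall.

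**5. Effect of prespecified adjustment on sample size.** If the covariates correlate r with PACU VAS, the n per arm for the same power is about 59 × (1 − r²). For r = 0.3 this is 59 × 0.91 = 53.7, so 54; for r = 0.5 it is 59 × 0.75 = 44.3, so 45 (r assumed). Prespecified adjustment therefore gives no reason to raise N.

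**The case against.** The strongest reply is that the primary analysis is already fixed. The SAP plans the t-test unconditionally, the power section rests on it ("Group sample sizes of 59 per group achieve 80% power to reject the null hypothesis of equal means"), and the stratified analysis is a later sentence most naturally read as supplementary. This largely stands. A reader might infer that the reported primary analysis itself depends on chance. The text does not support that, because it nowhere says that the stratified result replaces the t-test. Even if it did replace it whenever triggered, type I error in the simulations was 4.2% to 4.7%, below nominal.

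A reader might also infer that randomisation is planned without strata and that this is an error. The protocol is only silent; the REDCap set-up may contain strata. If it does not, simple 1:1 allocation still leaves the t-test valid. Nor do the documents show that facility, or a stent present before surgery, predicts VAS about one hour after arrival in the post-operative area. The background discusses symptoms from stents placed at surgery, which is planned for every participant. Care and anaesthesia are described as standard. An imbalance in stent status is quite possible: if 20% to 50% of patients are already stented (assumed), the chance of a difference above 10 points between arms of 59 is 17% to 28% under simple randomisation. Its effect on the outcome is unknown.

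Finally, the instinct behind the sentence has some merit. In the one-characteristic scenario (20% of variance explained), the unadjusted test rejected in 14.3% of the triggered null trials, against 4.7% for the adjusted test. But that depends on the characteristic predicting pain, which is the reason to choose covariates by prognosis in advance.

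What the reply does not answer is that the SAP gives no list, threshold, method or rank for a second analysis of the primary outcome.

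**Conclusion.** The point holds as a defect in specification. The imbalance-triggered analysis is data-dependent, selects covariates on the wrong ground, and has no stated status beside the t-test. One model fixed in advance is a better method at little cost.

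The numerical effect is small. Type I error is about 5.1% to 6.0% if the better of the t-test and the pooled result is reported. That range rests on assumed values: 1 to 15 binary characteristics, a 5% imbalance threshold, and 10% to 30% of VAS variance explained. It could be larger if the analysis were read as separate tests within strata, which the wording allows but does not state. The ambiguity over which result counts matters more than the error rate.

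The finding does not extend to the validity of the t-test, to the sample size, or to the absence of stated stratification factors, which is a design choice.

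**What to change.** In the SAP's analysis paragraph, before unblinding:
- Delete the imbalance-triggered sentence, or label that analysis exploratory.
- Name one primary analysis: a linear model of PACU VAS on treatment with fixed covariates. These are pre-operative VAS, indwelling stent at entry (yes/no) if recorded at screening, and any factors used to stratify allocation.
- Use heteroscedasticity-robust standard errors, because the power section assumes SDs of 1 and 2.5.
- Report the unadjusted unequal-variance t-test as a sensitivity analysis.
- State a simple rule for patients with missing pre-operative VAS, so that they are not dropped by default.

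In the protocol's randomization section, say whether the REDCap allocation is stratified and, if so, by what. Stratifying by stent status or facility is optional, and leaving it out is not an error.

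The cost is one SAP edit plus the missing-baseline rule. Pre-operative VAS is already collected, and applying the stent exclusion already requires stent status to be known. N stays at 59 per arm, about 200 in total at 40% dropout.

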### **CRITERIA FOR THERAPEUTIC RESPONSE/OUTCOME ASSESSMENT**

The intraoperative period is defined as the period from anesthesia induction to the extubation of the trachea. The surgical time is determined from the incision to the final skin closure.

The postoperative period is defined as the period from the extubation to various study endpoints.

Blood loss is defined as the estimate accounted from the suction device and absorptive sponges during the procedure, as described and agreed upon by the surgeon, anesthesiologist, circulating nurse, and surgical technician as covered by institutional guidelines.

The patient's pain will be evaluated with a visual analogue scale of pain [28]. This may either be done digitally or by paper [29].

Adverse events will be measured with an optional PACU questionnaire for nurses as well as by monitoring of unanticipated contact.

Neurological changes will be measured using the Watson[30] clock drawing test.

Satisfaction will be evaluated via questionnaires at subsequent time points.

Need for opioid pain medication will be carefully tracked via patient questionnaire, chart review, and review of any available prescription database.

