#### BIOSTATISTICS

#### Sample Size

The study will be powered with an 80% probability to detect a 10% difference in the primary outcomes. It will also assume a loss to follow up rate of 50%. This will require approximately 200 total subjects with a planned 1:1 placebo to active treatment enrollment ratio. We estimate at least 500 eligible procedures are conducted each year at our institution. Accounting for excluded patients and those who do not wish to participate, we estimate that full enrollment should be attainable within one year.

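### The plan expects to lose 40–50% of patients but names no analysis set or missing-data method, so its tests default to observed cases

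*SAP*

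**What the plan says.** The SAP's Power Analysis states: "Group sample sizes of 59 per group achieve 80% power". It uses a "two-sided two-sample unequal-variance t-test" and adds an "Assumption about 40% dropout rate" to reach about 200 patients. The protocol's Sample Size section reaches the same total from a different loss: "It will also assume a loss to follow up rate of 50" per cent.

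The SAP's analysis text lists a t-test for the primary VAS score, t-tests or chi-square tests for secondary outcomes, and generalized linear or logistic models with covariates. It describes the groups by treatment received. Neither document states an intention-to-treat rule, an imputation method or a missing-data sensitivity analysis. Missing data appear only in the protocol's Quality Assurance section, as a matter for data-quality reports.

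For opioid outcomes, the protocol's outcome-assessment section says: "Need for opioid pain medication will be carefully tracked via patient questionnaire, chart review, and review of any available prescription database". The evaluation schedule has staff chart reviews at 30 days and 1 year, but only patient questionnaires at 90 days and 6 months. Neither document says which source defines the outcome, or whether records count when a questionnaire is missing.

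**The concern.** Dividing the required number by the expected retention protects power. It does nothing for validity if the patients who are lost differ from those who stay, and differ unevenly between arms.

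There is a plausible route to uneven loss here. The protocol's background names temporary cognition and coordination changes as pregabalin's principal side effects. The primary VAS is supplied by the patient about an hour after arrival in the post-operative area, and the clock test is also done that day. A patient too drowsy to do either may be more likely to be on the active drug.

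For the clock test the direction is clear: if the most impaired patients cannot draw, the observed scores lean toward no cognitive harm. For pain it is not. Sedated patients could have more or less pain than those observed.

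The opioid outcomes raise a separate question. If a missing questionnaire were treated as a missing outcome, the proportions at 3, 6 and 12 months would rest on responders alone, although records could supply much of what is missing.

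**Working it through.** **Inputs from the SAP.** "significance level (alpha) of 0.05", two-sided; 80% power; "the population mean difference in VAS score is as little as 1 unit"; "standard deviations of 1 for group 1 (based on our pilot study) and 2.5 for group 2 (from literature"; 40% loss; about 200 patients, 1:1. **From the protocol:** 50% loss; about 6% new persistent opioid use after ureteroscopy (background).

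**1. Reproducing the plan's figures.**
- SE = √[(1² + 2.5²)/n] = √(7.25/n). At n = 59 this is 0.351. Welch power (noncentral t, Satterthwaite df) is 80.4%; at n = 58 it is 79.7%. So 59 per group is right.
- At 40% loss: 118/(1 − 0.40) = 197, consistent with about 200.
- At 50% loss: 118/(1 − 0.50) = 236, which is not about 200. With 200 enrolled, 50 per arm remain and power is 73.5%.

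**2. Bias in the observed-case comparison.** If a share f of the pregabalin arm is missing, and their mean VAS differs by s from those observed, the observed difference is off by f × s. Assume 40% missing in each arm, the SAP's SDs, no true effect, and no shift among missing placebo patients. With 60 observed per arm, SE = √(7.25/60) = 0.348:

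| Assumed shift s | Bias 0.4 × s | Bias/SE | Type I error |
|---|---|---|---|
| 0 | 0 | 0 | 5% |
| 0.5 units, either direction | 0.2 | 0.58 | 9% |
| 1 unit, either direction | 0.4 | 1.15 | 21% |

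The sign of s decides which arm the false rejections favour, not how many there are.

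**3. Tipping point.** An observed 1-unit benefit vanishes if missing pregabalin patients average 1/0.4 = 2.5 units higher than observed ones at 40% loss, or 1/0.5 = 2.0 units higher at 50% loss.

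**4. Loss that depends on the score itself.** Simulation under the null: 100 per arm, SD 2.5 in both arms, 4,000 runs. The correlation between VAS and going missing, and the loss by arm, are assumed.

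| Loss, pregabalin/placebo | Correlation | Bias (units) | Type I error |
|---|---|---|---|
| 50%/30% | 0.5 | −0.37 | 13.6% |
| 50%/30% | 0.3 | −0.22 | 7.6% |
| 50%/30% | 0 | about 0 | 5.0% |
| 40%/40% | 0.3 or 0.5 | about 0 | 5.0–5.4% |

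A positive correlation means that patients in more pain go missing more often. A negative one would reverse the sign of the bias.

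**5. Opioid proportion, if missing questionnaires meant missing outcomes.** Take 6% among responders. At 40% loss the all-randomised proportion lies between 0.06 × 0.60 = 3.6% and 3.6% + 40% = 43.6%. At 50% loss the bounds are 3.0% and 53.0%. These are the extremes, with no missing patient or every missing patient a user.

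**The case against.** A reader might infer that the plan prescribes a completers-only analysis. It does not: no sentence says so. The plan is silent, and use of observed cases is what the listed tests do when nothing else is specified.

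A reader might also take 40–50% as the share of primary VAS scores that will be missing after dosing. The documents do not say that. The primary measurement is made on the day of surgery and its completion is compensated, follow-up by questionnaire runs to one year, and the protocol speaks of loss to follow-up. The pilot reports that outcomes were tracked successfully. Loss before dosing, such as a cancelled operation, could not be drug-related. What survives is that both documents use the figure to size the primary comparison, and neither gives reasons for loss.

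The 21% type I error is not a forecast. It restates an assumed 0.4-unit bias. The 1-unit shift is a full SD in the pregabalin arm, since the SD of 1 comes from a pilot in which everyone took pregabalin, and nothing in the documents fixes its size or direction.

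On opioids, it would be wrong to say that the plan relies on questionnaires alone. Chart and prescription-database review are already planned. The gap is the unstated defining source, chiefly at 3 and 6 months, where the schedule lists only questionnaires.

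Finally, imputation from baseline variables would not by itself deal with loss caused by sedation, and the nurses' PACU questionnaire is optional. The REDCap instruments and clock-test instructions are not part of the text reviewed, so a field for the reason for non-completion may already exist.

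**Conclusion.** The point holds as a gap in specification. The plan anticipates 40% or 50% loss, two figures that cannot both lead to 200 patients, and offers only a larger sample in response. Without an analysis set or missing-data method, the tests default to observed cases.

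Drug-related loss is a reasonable inference from the protocol's own account of side effects and timing. It is not a documented fact, so the pain result could be biased in either direction, and the clock test could be biased toward no harm. Across the scenarios shown, type I error runs from about 5% (no shift, or equal loss by the same mechanism) to about 21% (1-unit shift in one arm). The missing fraction at the primary endpoint, the shifts, the correlations, the 50%/30% split and the common SD of 2.5 in the simulation are all assumptions.

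The primary VAS, clock score and satisfaction cannot be recovered from records. The opioid outcomes largely can, if the SAP says so. This should be corrected before the data are analysed.

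**What to change.** 1. **Analysis set.** State that all randomised patients are analysed in the arm assigned, replacing the wording by treatment received. Reconcile the 40% and 50% loss figures, and say how much loss is expected at the PACU assessment.
2. **Primary VAS.** Keep the observed-case comparison, adjusted for pre-operative VAS. Add a tipping-point analysis that varies the assumed mean of missing patients separately by arm. Multiple imputation from pre-operative VAS, age, sex and available PACU records can be its base case, but should not stand alone.
3. **Clock test.** Record why a test was not completed, and add a sensitivity analysis scoring patients who were unable to do it as the worst result.
4. **Opioid outcomes.** Define those at 30 days and 3, 6 and 12 months from the planned chart review and prescription-database data for every randomised patient, with questionnaires as a supplement.

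The cost is SAP wording, some analysis time and possibly one extra data field. One limit remains: records may miss opioids obtained outside the available databases.
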